### 8.3 POPULATIONS FOR ANALYSIS

Modified intention to treat. Only patients who participated in both drug administrations and have blood draws on at least 3 of the 4 required dates for each of the two administrations.

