### **3.5 CRITERIA FOR REMOVAL FROM PROTOCOL THERAPY AND OFF STUDY CRITERIA**

#### **3.5.1 Criteria for removal from protocol therapy**

- Completion of protocol therapy
- Participant requests to be withdraw from active therapy
- Unacceptable Toxicity as determined by the investigator
- Investigator discretion

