## **6 DATA COLLECTION AND EVALUATION**

### **6.1 DATA COLLECTION**

C3D and LABrador will be used for data collection purposes. The PI will be responsible for overseeing entry of data into an in-house password protected electronic system and ensuring data accuracy, consistency and timeliness. The principal investigator, associate investigators/research nurses and/or a contracted data manager will assist with the data management efforts. All data obtained during the conduct of the protocol will be kept in secure network drives or in approved alternative sites that comply with NIH security standards. Primary and final analyzed data will have identifiers so that research data can be attributed to an individual human subject participant.

*Abbreviated Title: Enzalutamide Formulation PK*  
*Version Date: 03.11.2020*

All adverse events, including clinically significant abnormal findings on laboratory evaluations, regardless of severity, will be followed until return to baseline or stabilization of event.

An abnormal laboratory value will be recorded in the database as an AE **only** if the laboratory abnormality is characterized by any of the following:

- Results in discontinuation from the study
- Is associated with clinical signs or symptoms
- Requires treatment or any other therapeutic intervention
- Is associated with death or another serious adverse event, including hospitalization.
- Is judged by the Investigator to be of significant clinical impact
- If any abnormal laboratory result is considered clinically significant, the investigator will provide details about the action taken with respect to the test drug and about the patient's outcome.

**End of study procedures:** Data will be stored according to HHS, FDA regulations, and NIH Intramural Records Retention Schedule as applicable.

**Loss or destruction of data:** Should we become aware that a major breach in our plan to protect subject confidentiality and trial data has occurred, this will be reported expeditiously per requirements in Section [7.2.1](#).

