### **8.2 SAMPLE SIZE DETERMINATION**

This study will be conducted as a two-period randomized crossover trial design. Patients will be randomized to initially receive the standard liquid filled soft gelatin formulation (Arm A) followed later by the liquid formulation, or the liquid formulation as the test product (Arm B)

Abbreviated Title: Enzalutamide Formulation PK  
Version Date: 03.11.2020

followed by the liquid filled soft gelatin formulation. A total of 12 evaluable patients will be randomized into the two arms. It has been identified that a decrease of approximately 30-40 ug\*h/mL in the AUC (less than a 20% decrease in the AUC for the test version vs. the standard formulation) would permit the two formulations to be considered bioequivalent, and it may be expected that the actual difference between the formulations may be a decline of approximately 10% (approximately 20 ug\*h/mL). When the sample size in each sequence arm is 6, (a total sample size of 12) a crossover design will have 80% power to reject the null hypothesis that the Arm B mean minus the Arm A mean is below -40 ug\*h/mL and the null hypothesis that the Arm B mean minus the Arm A mean is above 0 ug\*h/mL, i.e., that the two groups are not equivalent, in favor of the alternative hypothesis that the means of the two treatments are equivalent, assuming that the expected difference in means is -20 ug\*h/mL, the standard deviation of differences,  $s_d$ , is 20 ug\*h/mL, and that each test is made at the 5% level.

It is expected that approximately 1 patient per month may enroll onto this trial. Thus, to enroll 12 evaluable patients, it is anticipated that one year may be required. To allow for the possibility of a small number of patients who do not have full measurements obtained based on both drug administrations, the accrual ceiling will be set at 14 patients.

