#### 8.4.3 Analysis of the Secondary Efficacy Endpoints

The number of episodes of nausea and vomiting, as well as the grades of nausea and vomiting will be calculated and reported for each of the two formulations at each time point. The rates of grade 3 vomiting will be compared between the two formulations at each time point using Fisher's exact test.

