#### 8.4.4 Safety Analyses

Toxicity data: tabulated counts. The primary toxicity, nausea and vomiting, will be reported per arm at each of the time points when the drugs are administered.

*Abbreviated Title: Enzalutamide Formulation PK*  
*Version Date: 03.11.2020*

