#### 8.4.8 Tabulation of Individual Participant Data

None will be provided

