#### 10.1.6 Tolerability Assessment

To date, there is no available information on the palatability of the liquid enzalutamide preparation. Therefore, a brief tolerability assessment will be completed by each participant. Following the administration of the liquid (test) formulation, participants will be asked to complete [APPENDIX B](#)

Abbreviated Title: Enzalutamide Formulation PK  
Version Date: 03.11.2020

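### Section 8.3's only analysis population is a PK-completeness rule not limited to AUC; applied as written, it removes men who stop after one dose from the safety summaries

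*Combined protocol and SAP*

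**What the plan says.** **Population.** Section 8.3 labels its population modified intention to treat and then restricts it: "Only patients who participated in both drug administrations and have blood draws on at least 3 of the 4 required dates". The draw requirement must be met in both periods. By 8.1 the four dates are the AUC draw visits, Days 1, 3, 8 and 42. Section 8.3 does not tie the rule to AUC, and no safety population is defined elsewhere.

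**Safety summaries.** Under 8.4.3, episodes and grades of nausea and vomiting "will be calculated and reported for each of the two formulations at each time point", and grade 3 vomiting rates are compared by Fisher's exact test. Under 8.4.4, toxicity is given as counts, and nausea and vomiting "will be reported per arm at each of the time points when the drugs are administered". Neither section names a population or a denominator.

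**Related text.**
- Section 3.5.1 lists among the reasons for removal from therapy "Unacceptable Toxicity as determined by the investigator", and also the participant's own request.
- Section 8.2 sets an accrual ceiling of 14 for 12 evaluable men, to allow for "a small number of patients who do not have full measurements obtained based on both drug administrations".
- Section 8.4.8, on tabulating individual data, says "None will be provided".
- Section 10.1.6 says of the liquid that "a brief tolerability assessment will be completed by each participant".

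**The concern.** Whether enough draws were taken decides whether an AUC can be computed. It has no bearing on whether a man vomited after his dose. If the 8.3 rule governs the safety summaries, exclusion can be caused by the outcome being summarised: a man removed for a reaction to his first dose has no second administration, fails the rule, and takes his event with him. That can bias the event rate of the formulation he took downward. Since no individual tabulation is planned, the event would not surface in a listing either.

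Safety and tolerability is the secondary objective (1.1.2). The bias could fall on either formulation, but it matters more for the liquid, because 9.5 states that giving it without its capsule has not been evaluated for safety.

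**Working it through.** **1. Who fails 8.3 but has safety data.** Two kinds of men do:
- A man who stops after Period 1, by either 3.5.1 route above. He has one administration, and the rule requires two.
- A man who took both doses but missed two draw dates in a period. He has 2 of 4 dates, and the rule requires 3.

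**2. The plan's own number.** Section 8.2 asks for 12 evaluable men, for 80% power with two one-sided 5% tests. Inputs are limits of -40 and 0, a true difference of -20 and a standard deviation of differences of 20 (all ug\*h/mL). With standard error 20/√N and N − 2 degrees of freedom, power is 78.4% at N = 10 and 88.4% at N = 12. Twelve is thus the smallest balanced N that reaches 80%. It concerns AUC only, so a separate safety population leaves it unchanged.

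**3. Inputs for the illustration.** From the documents: 1:1 randomization with 6 to 7 men per arm (2.3.1), 12 evaluable men and a ceiling of 14 (8.2), and reporting at each time point (8.4.3, 8.4.4). Assumed: 7 men are randomized liquid-first; those who have grade 3 vomiting leave before Period 2; nobody else has it; and accrual ends with 12 evaluable men. The documents give no vomiting rate.

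**4. Period 1, liquid.** The rate is x/n with an exact (Clopper-Pearson) 95% interval. For zero events the upper limit is 1 − 0.025^(1/n): 1 − 0.025^(1/6) = 45.9% and 1 − 0.025^(1/5) = 52.2%.

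| Assumed case | All dosed men | 8.3 as written |
|---|---|---|
| One of 7 vomits and leaves | 1/7 = 14.3% (0.4 to 57.9) | 0/6 = 0% (0 to 45.9) |
| Two of 7 vomit and leave | 2/7 = 28.6% (3.7 to 71.0) | 0/5 = 0% (0 to 52.2) |

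**5. Pooled over periods.** Men dosed with the liquid are the 12 completers plus those who left.
- One leaves: 12 + 1 = 13, and 1/13 = 7.7% (0.2 to 36.0) reads 0/12 (0 to 26.5).
- Two leave: 12 + 2 = 14, and 2/14 = 14.3% (1.8 to 42.8) reads 0/12.

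The capsule denominator is 12 in both cases, because the men who left never took it.

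**6. The opposite direction.** If the excluded man only missed draws and had no event, while one other man vomited, the pooled rate rises slightly: 1/13 = 7.7% reads 1/12 = 8.3%. The rule does not always lower the rate. It does so when the reason for exclusion is linked to the event.

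**The case against.** The best case for the plan is that nobody would apply a blood-draw rule to vomiting. Section 8.4.4 has its own safety heading, and reporting at the occasions of dosing reads naturally as everyone dosed then. Section 10.1.6 has every participant complete the tolerability form. This is good evidence of intent, and a reader who inferred that the plan sets out to exclude these men would go beyond the text.

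It does not settle the matter. The 8.4.4 wording fixes when events are reported and by which grouping, not who is counted. The only stated population opens with a word that excludes everyone else. Sections 8.1 and 8.4.3 class safety among the secondary efficacy endpoints, which keeps the 8.3 reading open.

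A second tempting inference is that adverse events would go unrecorded or participants unprotected. The documents contradict it. Events are collected throughout both periods (3.3), and all of them, "regardless of severity, will be followed until return to baseline or stabilization of event" (6.1). The investigator reviews each patient's events (7.5.1), and expedited reporting (7.3) does not depend on 8.3.

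Three further limits stand. Much of the planned output is counts; the only rate explicitly compared is grade 3 vomiting, although whose events enter the counts is still open. The allowance in 8.2 is for incomplete measurements and does not mention toxicity. The reactions listed in 10.1.2.2 at 5% or more include neither nausea nor vomiting, so the illustrated cases may not occur.

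**Conclusion.** The point holds as a gap in the planned safety analysis. Section 8.3 supplies the only population, does not limit it to AUC, and would drop one-dose men and men with too few draw dates from the safety summaries if followed as written.

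At the ceiling of 14 with 12 evaluable, up to 2 of 14 dosed men (14.3%) could be left out. In the assumed cases a Period 1 liquid rate of 1/7 or 2/7 would read as zero. The intervals are wide and overlap heavily, so the harm is not a shifted inference. It is that an observed event can disappear from the table. The size rests on the assumed vomiting and withdrawal, and on accrual ending at 12 evaluable men, which is inferred from 8.2 and not stated as a stopping rule.

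The primary AUC analysis and its sample size are unaffected. The change should be made, because it is cheap and bears on a stated objective.

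**What to change.** In 8.3, limit the present population to the AUC analysis and add: 'Safety population: all men who received at least one dose, analysed by formulation taken; the denominator at each time point is the men dosed with that formulation in that period.' Name this population in 8.4.3 and 8.4.4.

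In 8.4.4, replace 'per arm' with 'per formulation'. Section 2.3.1 defines the arms as sequences, while 8.2 uses Arm A and Arm B means for the two formulations, so 'per arm' would leave the safety table ambiguous even with the population defined.

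The cost is a few words in three sections and no new data. Reported event rates may be higher than under the completer rule, and the formulations may have different denominators (for example 14 for the liquid and 12 for the capsule, pooled, if two liquid-first men leave).

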### 8.4 STATISTICAL ANALYSES

#### 8.4.1 General Approach

The difference in the AUCs will be calculated following a published non-parametric approach for analyzing data from two-period cross-over studies:

Koch GG "The Use of Non-parametric methods in the statistical analysis of the two-period change-over design. *Biometrics* 28: 577-584 (1972).

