#### **1.2.2 Pharmacokinetic Studies**

Multiple clinical pharmacokinetic studies of enzalutamide have been conducted [7]. Enzalutamide has a half-life of 5.8 days, achieves steady state by day 28, accumulates 8.3-fold with once-daily dosing, shows approximate dose proportionality from 30–360 mg/day, and has <30 % intersubject variability. It is primarily eliminated by hepatic metabolism, while renal excretion is an insignificant elimination pathway for enzalutamide and its active metabolite, N – desmethyl enzalutamide. Exposure to enzalutamide active moieties is not affected by food or baseline mild or moderate hepatic impairment. Enzalutamide has predictable pharmacokinetics, with low intersubject variability. Similar efficacy was observed in patients across the concentration/exposure range associated with a fixed oral dose of enzalutamide 160 mg/day.

*Abbreviated Title: Enzalutamide Formulation PK*  
*Version Date: 03.11.2020*

Study NCT01911715 was a phase I, open-label, one-period, single-dose mass balance and biotransformation study in six healthy male subjects [7]. After a single oral dose of enzalutamide 160 mg (4 x 40 mg capsules), at least 84.2% of the drug was absorbed. The average  $C_{max}$ ,  $t_{max}$ ,  $AUC_{inf}$ , and  $t_{1/2}$  of enzalutamide were 4.5 ug/mL, 1.8 h, 237 ug\*h/mL, and 2.9 days, respectively.

A phase I, open-label, randomized, single-dose, parallel design, food-effect study was performed in 60 healthy men (n=30 in fasted and fed arms) to determine the effect of a high-fat meal on the pharmacokinetics of enzalutamide [7]. The average  $C_{max}$  and  $T_{max}$  for the fasted and fed arms were 5.3 and 3.7 ug/mL and 1 and 2h post-dose, respectively. The average  $AUC_{inf}$  for the fasted and fed arms were 292 and 285 ug\*h/mL, respectively. In all, the data suggest that consumption of a high-fat meal slightly slows the rate of absorption but does not lower exposure of enzalutamide.

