#### 8.4.2 Analysis of the Primary Efficacy Endpoints

The average of the AUC values at the 4 determinations associated with each of the two drug administrations will be determined and the difference assessed for statistical significance at the 0.05 level using the non-parametric procedures identified in the Koch 1972 paper.

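### The 8.2 acceptance limit is given both as a percentage and in ug*h/mL, and the planned raw-AUC analysis produces no ratio or interval that answers the 20% question

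*Combined protocol and SAP*

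**What the plan says.** Section 8.2 gives the tolerated loss first as an absolute decrease of about 30-40 ug*h/mL and then, in parentheses, as "less than a 20% decrease in the AUC for the test version vs. the standard formulation". On the likely effect it says that "the actual difference between the formulations may be a decline of approximately 10" (per cent), put at roughly 20 ug*h/mL. The formal hypotheses are absolute only. One is "the null hypothesis that the Arm B mean minus the Arm A mean is below -40" (in ug*h/mL); its counterpart at the upper end places the same difference higher than zero. Power is worked out on that scale for a true difference of -20, an SD of differences of 20 ug*h/mL and 5% for each test.

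Section 8.4.1 sets the analysis: "The difference in the AUCs will be calculated following a published non-parametric approach for analyzing data from two-period cross-over studies". Section 8.4.2 has "the difference assessed for statistical significance at the 0.05 level" by that method. Neither section mentions a margin, a ratio, a log transformation or a confidence interval.

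Section 1.2.2 reports approximate dose proportionality and says that enzalutamide "has <30 % intersubject variability".

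**The concern.** A limit in ug*h/mL and a limit in per cent are the same limit at only one reference AUC. If the liquid loses a fixed fraction of the dose, each man's raw loss is that fraction times his own AUC. That is how residue in the syringe or incomplete extraction from the capsule would act. Raw differences then mix the formulation effect with between-man differences in clearance, and a fixed -40 stands for a different percentage loss at every reference AUC.

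Two things are at stake. A reader who wants to know whether the liquid loses less than 20% gets no planned estimate of that quantity. And if the 8.2 limit is applied to the 8.4 differences, the chance of accepting a true 20% loss depends on a reference mean that nobody controls.

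**Working it through.** **1. The plan's own sample size.** For a two-period crossover on raw differences with 6 men per sequence:

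SE = (s_d/2) × sqrt(1/6 + 1/6) = (20/2) × 0.577 = 5.77, with 10 degrees of freedom.

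Each bound lies 20 ug*h/mL from the expected -20, so the noncentrality is 20/5.77 = 3.46. Power for one bound is 94.2%, and for both it is 2 × 0.942 - 1 = 88.4%. With 5 per sequence it is 78.4%. So 12 is the smallest balanced total that reaches 80%. An SD of 22 would give exactly 80%. The planned number is sound on its own terms.

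**2. Do the two forms of the limit agree?**

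- 30/0.20 = 150 and 40/0.20 = 200, so they agree only at a reference AUC of 150-200.
- Fasted capsule, AUC day 1-7 (section 1.2.2): 40/185 = 21.6%.
- Mass balance study, AUCinf: 40/237 = 16.9%.
- Food-effect study, fasted AUCinf: 40/292 = 13.7%.

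**3. Error and power if the 8.2 bounds are applied.** Assumptions not in the documents: log-normal AUCs; a multiplicative formulation effect; an SD of within-man log(test/reference) of 0.10, which is about 20/200; and one AUC per man per period. The cited method is taken to be the rank-sum test on within-man period differences. Between-man CV is set at 30%, the ceiling in section 1.2.2, except where stated.

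To test a bound L, subtract L from the test-minus-reference differences in sequence AB, add L to the reference-minus-test differences in BA, and compare rank sums. With 6 against 6, the lower null is rejected at an AB rank sum of 50 or more (exact one-sided p = 0.0465). The upper null is rejected at 78 - 50 = 28 or less. Raw bounds are -40 and 0; log bounds are ln 0.80 and 0. Each cell has at least 50,000 simulated trials.

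| Reference AUC | Error at true ratio 0.80, raw | Error, log | Power at ratio 0.90, both bounds, raw | Power, log |
|---|---|---|---|---|
| 185 | about 17% | about 4.6% | 88% | 92% |
| 200 | about 8% | about 4.6% | 82% | 92% |
| 237 | about 1% | about 4.6% | 61% | 92% |
| 292 | 0.03% | about 4.6% | 29% | 92% |

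At reference AUC 200 and CV 15%, power is about 86.5% raw and 92% log.

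**4. How much of the gain comes from clearance?** At CV 0%, where men do not differ in clearance, power is still 88.1% raw and 91.6% log. That gain of 3.5 points is margin geometry. On the raw scale the expected effect is midway between the bounds, 20 from each. On the log scale ln 0.90 = -0.105 is 0.118 above ln 0.80 = -0.223, a little further from the lower bound.

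**5. Where does the 8% at AUC 200 come from?** There, -40 is exactly 20% of the arithmetic mean. The geometric mean at CV 30% is 200/sqrt(1 + 0.30²) = 191.6, and 20% of it is 38.3. With a limit of -38.3 the raw rank test has an error of about 4.8%.

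**6. The test as written in 8.4.2.** A two-sided test of no difference has a size of about 4.1% on either scale.

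**The case against.** The strongest reply is that the raw analysis matches the formal hypotheses. Both null values and the SD in 8.2 are in ug*h/mL, and the percentage stands in parentheses. That is correct, so it cannot be said that the plan defines bioequivalence only as a percentage. What remains is that 8.2 offers both forms as one limit, and they diverge at the reference AUCs the protocol itself cites.

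A reader might infer that the planned test accepts a 20% loss more than 5% of the time. The documents do not support this. Section 8.4.2 names no limit, and its no-difference test keeps its size. The inflation belongs to a test of the 8.2 limit on raw differences, which is the natural repair if 8.4 is brought into line with 8.2. It also reverses: above a reference AUC of about 200 the fixed -40 becomes conservative and costs power instead.

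A reader might also infer that raw differences inflate error whatever the limit. Step 5 shows otherwise for the rank test: the excess disappears when the limit is taken from the geometric mean, although a loss of power remains. Nor is the whole gain from logs due to clearance (step 4). Testing the lower bound alone gives about 89% raw and 97% log, but 8.2 requires both bounds, and on that basis the raw analysis at AUC 200 still exceeds the planned 80%.

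The log scale is not better under every model. If the liquid lost a constant number of ug*h/mL from every man, the raw analysis would hold 5% error and 88% power, and a log t-test would fall to 84% at CV 20% and 74% at CV 30%. Nothing in the documents suggests such an effect, and the reported dose proportionality points the other way.

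Finally, the protocol calls this a pilot and disclaims labelling use, which limits the consequences.

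**Conclusion.** The point holds as a mismatch between limit and analysis scale. The two forms of the limit in 8.2 need reconciling, and 8.4 should produce a test/reference ratio with an interval. The size depends on a proportional effect, log-normal AUCs and a log SD near 0.10. On those assumptions, with CV 30%, applying -40 to raw differences gives an error at a true 20% loss anywhere from about 17% to well under 1% over reference AUCs of 185-292. The log scale holds it at about 4.6%. At AUC 200 the log analysis gains about 10 points of power at CV 30% and 5 to 6 at CV 15%, of which about 3.5 are margin geometry. CV 30% is a ceiling, so the figures based on it are towards the upper end.

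This is a change that should be made. It does not show that the test now written in 8.4.2 has an inflated error rate. Taking logs would not by itself give 8.4.2 an equivalence decision rule, so both changes belong together.

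**What to change.** In 8.4.1 and 8.4.2, take the natural log of each man's AUC in each period and apply the same rank-based crossover method to the within-man log differences. Report the back-transformed test/reference ratio with a 90% confidence interval. Declare equivalence only if that interval lies within the 8.2 limits.

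In 8.2, restate every input on the same scale: a lower bound of 0.80; the upper bound of 0 as a ratio of 1.00, unless the sponsor revises it; an expected ratio of 0.90; and an SD of log differences with its source. Then recalculate power. The SD matters: with t-based tests of both bounds and 12 men, power is about 94% at a log SD of 0.10, 82% at 0.12 and 55% at 0.15.

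The cost is protocol wording and one recalculation, with no added patients, samples or visits. The downside is the loss of power noted above if the effect proved to be a constant amount.
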